8.3.2 TREATMENT GROUP ASSIGNMENT

All eligible subjects will receive RA101495.

8.3.3 BLINDING

This is an open-label study.

8.4 DISCONTINUATION CRITERIA

8.4.1 DISCONTINUATION OF INVESTIGATIONAL MEDICINAL PRODUCT

If a subject prematurely discontinues the investigational medicinal product (IMP), RA101495, at any time prior to completion of the Day 84 Visit during the Treatment Period, the subject should return to clinic for an End-of-Study Visit. The following procedures will be completed at this visit:

- Review and documentation of concomitant medications
- Physical examination, including weight
- Vital signs (heart rate, body temperature, blood pressure) in the sitting position after resting for at least 5 minutes
- 12-lead ECG in a supine position (lying down) for at least 5 minutes prior to, and during, the recording

- Blood samples for clinical chemistry, hematology, coagulation, and PNH clone size
- Urine sample for urinalysis
- Serum pregnancy for females of childbearing potential only
- Return of electronic diary (e-diary) to site
- Completion of QOL questionnaires
- Completion of treatment satisfaction questionnaire
- Record AEs
- Blood samples for:
 - PK analysis
 - PD analysis
 - ADA determination
 - Additional biomarkers
- Return of all used and unused study drug syringes and injection device to site

8.4.2 WITHDRAWAL FROM THE STUDY

Subjects who are withdrawn from the study must promptly discontinue treatment with RA101495, and make every effort to return to the clinic to complete an End-of-Study Visit, as described in [Section 8.4.1](#). All unused study drug syringes must be returned to the clinic as described in [Section 10.2](#).

8.5 EARLY STUDY TERMINATION

The Sponsor may terminate this study early, either in its entirety or in part or at one or more study sites, for reasonable cause provided that written notice is submitted in advance of the intended termination. The investigator may also terminate the study at the site for reasonable cause, after providing written notice to the Sponsor in advance of the intended termination. Advance notice is not required by either party if the study is stopped due to safety concerns. If the Sponsor terminates the study for safety reasons, the Sponsor will immediately notify the investigator and subsequently provide written instructions for study termination.

8.6 END OF STUDY

The end-of-study is defined as the date of the last subject's last visit. Subjects who complete the Treatment Period, and are deriving benefit from RA101495, will have the option to enter a long-term extension study.

9 SELECTION OF STUDY POPULATION

9.1 INCLUSION CRITERIA

To be eligible for this study, subjects must meet **ALL** of the following inclusion criteria:

1. Male or female ≥ 18 years
2. Completed informed consent procedures, including signing and dating the informed consent form (ICF).
3. Diagnosis of PNH by flow cytometry
4. Inadequate response to eculizumab defined as having received eculizumab for at least 6 months plus one or more of the following criteria:
 - A documented lactate dehydrogenase (LDH) level ≥ 1.5 x the ULN within 90 days prior to Screening
 - Presence of a known C5 mutation conferring resistance to eculizumab
5. Female subjects of child bearing potential must have a negative pregnancy test at Screening and within 24-hours prior to the first dose of RA101495
6. Sexually- active female subjects of child-bearing potential (i.e. women who are not post-menopausal or who have not had a bilateral oophorectomy, hysterectomy, or tubal ligation) and all male subjects (who have not been surgically sterilized by vasectomy) must agree to use effective contraception during the study. Effective contraception is defined as:
 - Hormonal contraception (e.g. oral contraceptive, transdermal contraceptive, contraceptive implant, or injectable hormonal contraceptive) for at least 3 months prior to study drug administration, throughout the study, and for 4 weeks after the last dose of study drug.
 - Double-barrier birth control (e.g. male condom, female condom, diaphragm sponge, or cervical cap together with spermicidal foam/gel/film/suppository) starting at the Screening Visit, throughout the study, and for 4 weeks after the last dose of study drug.
 - Intrauterine contraception/device starting at the Screening Visit, throughout the study, and for 4 weeks after the last dose of study drug.
 - Total abstinence from sexual intercourse for at least one complete menstrual cycle prior to the Screening Visit, throughout the study, and for 4 weeks after the last dose of study drug
 - Maintenance of a monogamous relationship with a male partner who has been surgically sterilized by vasectomy.

9.2 EXCLUSION CRITERIA

Subjects who meet **ANY** of the following exclusion criteria must be excluded from the study:

1. Platelet count $<30,000/\mu\text{L}$ or absolute neutrophil count (ANC) <500 cells/ μL at Screening
2. Calculated glomerular filtration rate of <60 mL/min/ 1.73m^2 based on modification of diet in renal disease (MDRD) equation at Screening
3. Elevation of liver function tests defined as direct bilirubin $>1.5\text{xULN}$ or elevated transaminases (ALT or AST $>1.5\text{xULN}$)
4. Elevation of amylase or lipase $>2\text{xULN}$
5. History of meningococcal disease
6. Current systemic infection or suspicion of active bacterial infection
7. Pregnant, planning to become pregnant, or nursing female subjects
8. Recent surgery requiring general anesthesia within the 2 weeks prior to Screening, or expected to have surgery requiring general anesthesia during the 12-week Treatment Period
9. Active malignancy requiring surgery, chemotherapy, or radiation within the prior 12-months (subjects with a history of malignancy who have undergone curative resection or otherwise not requiring treatment for at least 12-months prior to Screening with no detectable recurrence are allowed)
10. History of any significant medical or psychiatric disorder that in the opinion of the investigator would make the subject unsuitable for participation in the study
11. Treatment with any investigational medicinal product or investigational device within the 30 days prior to Screening or participation in another concurrent clinical trial involving a therapeutic intervention (participation in observational studies and/or registry studies is permitted)
12. Unable or unwilling to comply with the requirements of the study

9.3 REMOVAL AND REPLACEMENT OF SUBJECTS IN THE STUDY

9.3.1 PREMATURE DISCONTINUATION

Every reasonable effort should be made to encourage retention of subjects in the study, maximize compliance with study drug, and facilitate attendance at all scheduled study visits.

All subjects have the right to refuse further participation in the study at any time and for any reason. A subject's participation must, therefore, be terminated immediately upon his/her request.

The investigator will make every attempt to ascertain the reason(s) for discontinuation and to document this in detail in the source documentation and the appropriate sections of the electronic case report form (eCRF). Subjects may be withdrawn from the study due to any of the following reasons:

- Subject withdraws consent
- Subject is non-compliant, defined as refusal or inability to adhere to the study procedures
- Unacceptable or intolerable treatment-related AEs
- Use of any other investigational treatment
- Any illness or circumstance (e.g. incarceration) that would substantially impact the study procedures or outcome measures
- At the request of the Sponsor, regulatory agencies, or independent ethics committee (IEC)/institutional review board (IRB)
- Loss to follow-up

9.3.2 REPLACEMENT OF SUBJECTS

Enrolled subjects who prematurely discontinue study treatment for any reason prior to the Day 84 Visit may be replaced, at the discretion of the Sponsor, in order to obtain an adequate number of evaluable subjects (see [Section 13.2](#)).

10 INVESTIGATIONAL MEDICINAL PRODUCTS AND TREATMENTS

10.1 STUDY TREATMENT ADMINISTRATION

10.1.1 IDENTITY OF INVESTIGATIONAL MEDICINAL PRODUCT AND TREATMENT

The investigational medicinal product (IMP) RA101495 will be supplied as a sterile, preservative-free, aqueous solution pre-filled into 1 mL glass syringes with a 29 gauge ½ inch staked needle placed within a self-administration device.

Subjects will be instructed to self-administer SC doses daily. The dose (dose volume) for each injection will depend on the dose requirement and subject's bodyweight (see Section 10.1.3 and Section 10.1.4).

10.1.2 TREATMENT GROUPS

All eligible subjects will receive a single loading dose of 0.3mg/kg RA101495 SC followed by study drug at 0.1 mg/kg SC once daily.

10.1.2.1 DOSE ESCALATION

After 2 weeks of treatment with RA101495 at 0.1 mg/kg, if a subject has not achieved an adequate response (defined as an LDH <1.5xULN), the dose should be escalated to 0.3 mg/kg daily. Dose escalation may proceed only if no severe (i.e. Grade ≥3) or serious treatment-emergent adverse events are reported at the 0.1 mg/kg dose.

For subjects who have a dose increase to 0.3 mg/kg, samples for PK and PD should be collected at pre-dose of the first day of the new dose, then at scheduled visits per the Time and Events Table (Table 1).

10.1.3 DOSING SCHEDULE

The Day 1 Visit should be scheduled to coincide with the next scheduled dose of eculizumab (i.e. 14 ± 2 days after from the last eculizumab dose). Eculizumab should NOT be administered on the Day1 Visit or at anytime thereafter during the study.

All subjects will receive a loading dose of 0.3mg/kg dose of RA101495 on Day 1, which will be administered during the study visit by the site staff. During the remainder of the Treatment Period, subjects will self-administer the daily dose (0.1 mg/kg or 0.3 mg/kg) every 24 hours at approximately the same time each day. On days of the scheduled study visit at the investigator site, the dose must be administered after the blood work is completed at the investigator site.

10.1.4 DOSE PRESENTATION

Doses of RA101495 will be determined by a target dose and weight, accomplished using a fixed dose by weight brackets. These brackets are grouped by bodyweight category such that each subject will receive the no less than the target minimum dose to avoid sub-therapeutic dosing. For the 0.1 mg/kg dose, subjects will receive, at a minimum, a fixed dose of 0.1 mg/kg (range

0.10 to 0.14 mg/kg). For the 0.3 mg/kg dose level, subjects will receive a minimum dose of 0.3 mg/kg (range 0.3 mg/kg to 0.41 mg/kg). Table 3 summarizes dose presentations for RA101495 0.1 mg/kg and 0.3 mg/kg doses. Subjects who present with a higher body weight (>109 kg) will be accommodated on a case-by- case basis, in consultation with the medical monitor.

Table 3 Dose Presentations by Weight Brackets

Target Dose (mg/kg)	Dose Presentation			Weight Range (kg)	Dose Range (mg/kg)
	Fill Volume		Dose		
	Number	mL	mg		
0.1	1	0.150	6	≥43 to <61	0.10 to 0.14
0.1	2	0.220	8.8	≥61 to <88	0.10 to 0.14
0.1	3	0.310	12.4	≥88 to <109	0.11 to 0.14
0.3	4	0.416	16.6	≥43 to <56	0.30 to 0.39
0.3	5	0.574	23	≥56 to <77	0.30 to 0.41
0.3	6	0.810	32.4	≥77 to <109	0.30 to 0.42

10.1.4.1 MISSED DOSES

If a subject misses one dose (i.e. 1 day) of RA101495, the subject should document the missed dose in his/her subject e-diary and take the next planned dose as scheduled. The subject should contact the investigator as soon as possible. If a subject misses 2 or more doses, the subject must notify the investigator immediately.

10.2 STUDY TREATMENT MANAGEMENT

10.2.1 PREPARATION AND DISPENSING

Pre-filled syringes will be dispensed to each subject every 2 weeks, beginning on Day 1 of the Treatment Period.

Subjects will be provided training and detailed instructions regarding administration of RA101495 using the pre-filled syringes and the injection device will be supplied in a separate manual.

10.2.2 STUDY DRUG SUPPLY, STORAGE, AND HANDLING

RA101495 will be provided as a sterile, preservative-free, aqueous solution for injection containing 40 mg/mL of active ingredient, RA101495, in a formulation of 50 mM sodium phosphate and 76 mM sodium chloride at a pH of 7.0 pre-filled into a 1 mL glass syringe with a ½ inch, 29 gauge staked needle. Six dosage strengths will be supplied as shown in Table 3.

The IMP should be stored at 2 °C to 8°C.at the study site. Once dispensed to subjects, the IMP may be stored at controlled room temperature (20°C to 25°C [68°F to 77°F]) for up to 30 days protected from sources of heat, light and damage. Storage of IMP outside of room temperatures should be avoided.

Subjects will be instructed to self-inject SC doses daily every 24 hours at approximately the same time each day. The subject will be provided with an injection device for use during the study. Subject may inject in the abdomen (preferred site), thigh or upper arm.

All subjects will receive a study drug kit that will include RA101495 prefilled syringes, a syringe disposal container, alcohol wipes, and adhesive dressings.

10.2.3 DISPOSAL, RETURN, OR RETENTION OF UNUSED DRUG

At all visits, subjects will also receive a secure container to dispose of used syringes while at home. At each visit the subject should bring the used container containing all used syringes to be returned to the site. The unused study drug (unused syringes) should be retained by the subject and be used first in the immediate two weeks.

All study drug (syringes) and disposal containers must be returned to the site at the last study visit.

10.2.4 DRUG ACCOUNTABILITY

An e-diary where the subject documents study drug administration will be used to reconcile accountability during the study. The number of study drug syringes dispensed, used, and returned will be documented.

10.3 COMPLIANCE

Subjects will be required to record the date, time, and location of injections each day in an e-diary. The e-diary entries will be evaluated to determine compliance with study drug administration. If a subject does not confirm daily dosing using the e-diary, the investigator will receive an automated notification to contact the subject.

11 STUDY ASSESSMENTS

Please refer to [Table 1](#) for the timing of study assessments.

11.1 SUBJECT AND BASELINE DISEASE CHARACTERISTICS

11.1.1 DEMOGRAPHIC DATA

The following demographic data will be collected: date of birth, gender, ethnicity, and race.

11.1.2 DISEASE AND PRIOR TREATMENT HISTORY

A detailed history of PNH for a minimum of 6 months prior to Screening will be obtained, including (but not limited to) the following data: date of diagnosis, PNH clone size at diagnosis (if available), history of thrombotic events, history of transfusions, and history of PNH-specific prior therapy (e.g. immunosuppressives, anticoagulants, associated bone-marrow disorders).

The date eculizumab treatment was initiated and dose received will be documented. A dosing history for each subject (including dates and all dosage changes for a minimum of 6 months prior to Screening) will also be recorded.

11.1.3 PRIOR AND CONCOMITANT MEDICATIONS

All prescriptions and over-the-counter medications taken during the 30 days prior to the Screening Visit will be documented.

Concomitant medications include any prescription or over-the-counter medication that is ongoing on Day 1 or that is initiated following the first dose of study drug on Day 1.

Findings will be recorded on the subject's source documents and entered on the appropriate eCRF. Any changes to concomitant medications during the Treatment Period will be recorded in the eCRF.

11.2 SAFETY ASSESSMENTS

11.2.1 MEDICAL AND SURGICAL HISTORY

Relevant medical history will be documented to assess subject eligibility.

Detailed medical history regarding the occurrence of specific events or conditions (e.g. underlying bone marrow pathology, major vascular events, pulmonary hypertension, impaired renal or hepatic function, infections, malignancies) for a minimum of 6 months prior to Screening will also be collected.

11.2.2 PHYSICAL EXAMINATION

Physical examinations will include the following assessments:

- General inspection

- Weight (kg) and height (height in cm to be collected at Screening Visit only)
- Examination of the injection site and draining nodes
- Head/ears/eyes/nose/throat examination
- Mucosal examination for icterus
- Cardiac examination
- Auscultation of lungs
- Abdominal examination (liver, spleen, and lower abdomen)
- Assessment for neurological deficits
- Musculoskeletal assessment

Any abnormalities found will be recorded in the eCRF.

11.2.3 VITAL SIGNS

Vital signs (heart rate, body temperature, and blood pressure) will be measured in the sitting position after resting for at least 5 minutes. If blood samples are scheduled at the same time, vital signs should be measured before the blood draw. Blood pressure may be measured manually or by automated device, preferably in the non-dominant arm. The same measurement technique should be used throughout the study for all subjects. Temperature will be measured with an electronic device.

11.2.4 ELECTROCARDIOGRAM

Subjects should be in a supine position (lying down) for at least 5 minutes prior to and during the 12-lead ECG recording. ECGs will be assessed as normal or abnormal by the investigator; any abnormal findings will be described in the eCRF and the investigator will assess clinical significance. The ECG recording strip will be signed and dated by the investigator and stored in the medical records.

ECGs should be performed prior to blood draws when both assessments are completed (see [Table 1](#)).

11.2.5 NEISSERIA MENINGITIDIS TESTING

All subjects must have a negative result for *Neisseria meningitides* colonization via a throat swab prior to study entry. The throat swabs for *Neisseria meningitidis* will be obtained at Screening and sent to a certified laboratory for analysis to confirm absence of colonization.

All subjects must have documentation of prior *Neisseria meningitidis* vaccination (and booster if appropriate) prior to study entry.

11.2.6 ADVERSE EVENT RECORDING

Guidance on the identification, monitoring, and reporting of AEs is provided in [Section 12](#).

11.2.7 LABORATORY SAFETY ASSESSMENTS

11.2.7.1 BLOOD CHEMISTRY AND HEMATOLOGY

Clinical chemistry and hematology analytes to be collected are identified in Table 4 and should be performed as specified in the Time and Events Table 1. All coagulation tests should be performed as per standard practice on any subject taking anticoagulant therapy in addition to specified assessments in this schedule of events.

Table 4 Clinical Chemistry, Hematology, and Coagulation Analytes

Clinical Chemistry	Hematology
alanine aminotransferase (ALT)	free hemoglobin
albumin	haptoglobin
alkaline phosphatase (ALP)	hematocrit
amylase	hemoglobin
aspartate aminotransferase (AST)	mean corpuscular hemoglobin (MCH)
bicarbonate	mean corpuscular hemoglobin concentration (MCHC)
bile acids	mean corpuscular volume (MCV)
bilirubin (total, direct, and indirect)	platelet count
blood urea nitrogen (BUN)	RBC count
calcium	reticulocyte count
chloride	white blood cell (WBC) count and differential (%)
creatinine	Coagulation
gamma-glutamyl transferase (GGT)	international normalized ratio (INR)/prothrombin time (PT)
glucose	fibrinogen
lactate dehydrogenase (LDH)	partial thromboplastin time (PTT) or activated partial thromboplastin time (aPTT or APTT)
lipase	Other
potassium	C-reactive protein (CRP)
sodium	creatinine phosphokinase (CPK)
total protein	
uric acid	

11.2.7.2 URINALYSIS

A urinalysis will be performed to measure pH, specific gravity, protein (qualitative), glucose (qualitative), ketones (qualitative), bilirubin (qualitative), urobilinogen, occult blood, hemoglobin, and cells. A microscopic examination will be performed, if necessary. Hemoglobinuria will be assessed using a urine colorimetric scoring system.

11.2.7.3 PREGNANCY TEST

A serum pregnancy test for human chorionic gonadotropin will be performed on female subjects of childbearing potential at Screening.

A urine dipstick pregnancy test (human chorionic gonadotropin) will be performed on female subjects of childbearing potential at Day 1 pre-dose and Day 29, Day 57, and Day 84 (End of Study).

11.2.8 PNH CLONE

Blood sample for measurement of PNH clone size will be collected at Screening and Day 29, Day 57, and Day 84 (or End-of-Study Visit). PNH clone size will be determined by peripheral blood flow cytometry analysis (RBCs and granulocytes).

11.2.9 IMMUNOGENICITY

A multi-tiered ADA testing approach has been implemented according to FDA Guidance for Industry (Assay Development and Validation For Immunogenicity Testing Of Therapeutic Protein Products, April 2016).

Blood samples for ADAs will be collected prior to dosing on Day 1 and on Day 29, Day 57, and Day 84 (or at the End-of-Study Visit) in all enrolled subjects. These samples will be banked and used to investigate and characterize any ADA response over time in the general study population.

Samples will be sent to a central laboratory to determine the presence or absence of antibodies against RA101495 using an initial screening assay based on an ELISA format. Samples testing positive are then subjected to a confirmatory assay. Confirmed positives are then further characterized by titering. Neutralizing antibodies will then be confirmed using a bioassay of inhibition of sheep red blood cell hemolysis.

In the event of unexplained alterations in drug concentrations of RA101495 or loss of efficacy in previously well-controlled patients, determination of ADA (including assay for neutralizing ADA) will be made. Should a patient develop neutralizing ADA, the impact on RA101495 pharmacokinetics will be considered in consultation with the medical monitor, along with all other case details, to determine if the subject should continue study treatment. Further blood samples may also be taken over time to monitor titer and/ or resolution.

Analysis of immunogenicity will include a subset analyses of 1) subjects with confirmed ADA and 2) subjects with neutralizing ADA in which data from these subjects are compared to a) the

entire safety population and b) subjects without confirmed ADA. Analyses of PK, PD, safety and efficacy (as defined in the statistical analysis plan) will be included in the subject analyses

Detailed instructions regarding sample collection, processing, and shipping will be provided in a separate laboratory manual.

11.3 EFFICACY ASSESSMENTS

Efficacy assessments include the measurement of serum LDH levels as a measure of intravascular hemolysis. Additional assessments will include laboratory assessments of total bilirubin, total hemoglobin, free hemoglobin, haptoglobin, reticulocytes, and hemoglobinuria.

11.4 PHARMACOKINETIC AND PHARMACODYNAMIC ASSESSMENTS

Blood samples for the measurement of plasma concentrations of RA101495 and metabolites will be collected on all subjects. All subjects will also have a blood sample for measurement of eculizumab plasma concentrations.

Blood samples for pharmacodynamic assessments will be collected on all subjects and include measurement of:

- CH₅₀
- sRBC lysis for classical complement pathway
- Wieslab ELISA for alternative complement pathway
- C5 levels

Blood samples for PK and PD will be collected at the following time points in relationship to the first dose of RA101495: pre-dose (within 1 hour before first dose administration) and at 1, 3, and 6 hours post-dose on Day 1. For subjects who have a dose increase to 0.3 mg/kg, samples for PK and PD should be collected at pre-dose Day 1 of the new dose.

Blood samples for PK of eculizumab should be collected at screening, Day 1, Day 15, Day 29, and Day 43. The sample should be collected prior to administration of RA101495.

All samples will be sent to a central laboratory for analysis. Detailed instructions regarding PK and PD sample collection, processing, and shipping will be provided in a separate laboratory manual.

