- b. The Day 1 Visit should be scheduled to coincide with the next scheduled dose of eculizumab (i.e. 14 ± 2 after from the last eculizumab dose). Eculizumab should NOT be administered at the Day 1 Visit or at any time thereafter during the study.
- c. Height will be measured only at the Screening Visit.
- d. All subjects must have a negative throat swab for *Neisseria meningitidis* colonization for eligibility. All subjects must have documentation of prior *Neisseria meningitidis* vaccination (and booster if appropriate) prior to study entry.
- e. Including LDH for primary efficacy endpoint
- f. Coagulation tests should be performed, according to standard practice, on all subjects taking anticoagulant therapy.
- g. For all female subjects of childbearing potential, a negative serum pregnancy test must be documented at the Screening Visit and a negative urine pregnancy test must be documented at the Day 1 Visit prior to dosing. All other pregnancy tests will be urine.
- h. All AEs and SAEs should be monitored until resolution or stabilization. SAEs that occur within 30 days after last dose of study drug should be reported using the procedures outlined in section 12.3.1.2. These SAEs should be recorded in the CRF for this study for subjects who do not enroll in the extension study, and recorded in the extension study CRFs for subjects who enroll in the extension study.
- i. The injection site should be assessed at each clinic visit through Day 84 (End of Study).
- j. Blood samples for PK and PD and additional biomarker sampling at the following time points in relationship to the first dose of RA101495: pre-dose (within 1 hour before first dose administration) and at 1, 3, and 6 hours post-dose on Day 1. For subjects who have a dose increase to 0.3 mg/kg, samples for PK and PD should be collected at pre-dose Day 1 of the new dose, see footnote j. On clinic visit days PK and PD should be collected prior to administration of RA101495.
- k. Blood samples for PK of eculizumab should be collected at screening, Day 1, Day 15, Day 29, and Day 43 (2-week, 4-week, and 6-week) Visits. The sample should be collected prior to administration of RA101495.
- l. Blood sample for ADA on Day 1 must be obtained prior to dosing of RA101495.
- m. Blood sample for optional pharmacogenomic testing must be obtained on Day 1.
- n. On clinic visit days, the study drug RA101495 should be administered after blood samples for PK and PD are collected.

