6.3 CLINICAL TRIAL EXPERIENCE WITH RA101495

Clinical trial experience with RA101495 to date includes a single Phase 1 study (RA10145-1001) in healthy volunteers. The study RA101495-1001 was a randomized, double-blind, placebo-controlled, single-ascending-dose (SAD) and multiple-dose (MD) study designed to evaluate the safety, pharmacokinetics (PK), and pharmacodynamics (PD) of RA101495.

The first part of the study (SAD) evaluated a single dose of RA101495 versus placebo at 4 dose levels (0.05, 0.1, 0.2 and 0.4 mg/kg) in separate cohorts. The SAD enrolled 22 subjects; 14 received RA101495 (0.05 mg/kg in two subjects; 0.1, 0.2 and 0.4 mg/kg in four subjects each) and eight subjects received placebo, two per each dose level.

The second part of the study (MD) evaluated 7 daily doses of RA101495 versus placebo at a single dose level (0.2 mg/kg). The MD enrolled six subjects; four received RA101495 and two received placebo.

RA101495 when administered as a single dose and with 7-day repeat dosing displayed consistent and predictable PK that tightly correlated with the PD effect (inhibition of hemolysis and suppression of complement activity).

The plasma concentrations of RA101495 following single-dose SC administration (SAD) showed dose-dependent increases across all dose levels examined (0.05, 0.1, 0.2, and 0.4 mg/kg) (Figure 3). The mean C_{max} ranged from 1010 to 5873 ng/mL across doses. The mean AUC_{0-24} ranged from 21,440 to 112,300 ng* h/mL across doses. The mean half-life ($t_{1/2}$) was consistent across dose levels and ranged from 155.6 to 185.4 hours.

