7.2.3 PHARMACOKINETIC

- Plasma concentrations of RA101495 and its major metabolites
- Maximum plasma concentration (C_{max})
- Time corresponding to C_{max} (t_{max})
- Area under the drug concentration-time curves (AUC_{0-t})
- Plasma concentrations of eculizumab

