13.3.6 CLINICAL PHARMACOLOGY ANALYSIS

13.3.6.1 PHARMACOKINETIC ANALYSIS

Drug exposure will be evaluated using PK parameters derived from non-compartmental methods. All calculations for the final analysis will be based on actual sampling times. Individual PK parameters will be presented in listings and summarized using descriptive statistics.

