3.9.4 Pharmacokinetic Endpoints Analysis

The following pharmacokinetic endpoints will be summarized using descriptive statistics:

- Plasma concentrations of RA101495 and its major metabolites
 - Maximum plasma concentration (C_{\max})
 - Time corresponding to C_{\max} (t_{\max})
 - Area under the drug concentration-time curves (AUC_{0-t})
- Plasma concentrations of eculizumab.

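### Do Cmax, tmax and AUC0-t need a stated dose, day and end time, given that post-dose sampling covers only six hours on Day 1?

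*Protocol*

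**What the plan says.** Protocol 7.2.3 lists plasma concentrations, Cmax, tmax and "Area under the drug concentration-time curves" (AUC0-t). Protocol 13.3.6.1 gives the method: "Drug exposure will be evaluated using PK parameters derived from non-compartmental methods", based on actual sampling times. SAP 3.3.5 repeats this, and SAP 3.9.4 adds only that "The following pharmacokinetic endpoints will be summarized using descriptive statistics". None of these sections names a dose, a day or t.

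The sampling is set out elsewhere:

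- **Day 1, loading dose of 0.3 mg/kg:** "pre-dose (within 1 hour before first dose administration) and at 1, 3, and 6 hours post-dose on Day 1" (Protocol 11.4).
- **Later visits:** "On clinic visit days PK and PD should be collected prior to administration of RA101495" (Protocol Table 1, footnote j). Protocol 10.1.3 agrees: "the dose must be administered after the blood work is completed at the investigator site".
- **Escalation to 0.3 mg/kg daily:** "samples for PK and PD should be collected at pre-dose of the first day of the new dose" (Protocol 10.1.2.1), followed by the scheduled visits.
- **Early End-of-Study Visit:** one PK sample with no stated time since dose (Protocol 8.4.1).

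The post-lock SAP amendment (section 2.1) splits the concentration tables into those before and those after escalation, and a footnote says that the first set includes the loading dose. Its list of tables leaves the PK parameter table, 14.2.12, unmodified, with no dose or day in the title.

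**The concern.** PK is a stated objective, and 14.2.12 is the only PK parameter table. Taken literally, AUC0-t could mean two things: the area over the Day 1 profile, with t = 6 h, or the area from the first dose to the last sample in Week 12. The second would run the loading dose, 0.1 mg/kg daily and possibly 0.3 mg/kg daily together in one number. It could also report a pre-dose value as Cmax, with a tmax of weeks. Neither version gives Cmax, tmax or AUC within a maintenance dosing interval.

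Elsewhere the Protocol does name the interval: it writes AUC0-24 or AUCtau in 6.3 and in Table 2. The missing label could therefore look like an undefined endpoint.

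**Working it through.** **1. Check of the Phase 1 inputs (Protocol 6.3 and Table 2).**
- CL/F at 0.2 mg/kg on Day 7 = dose / AUC = 200,000 / 151,300 = 1.32 mL/h/kg (stated: 1.3).
- Day 7 over Day 1: Cmax 7.29 / 2.533 = 2.88 (stated: about 2.9); AUC 151.3 / 50.01 = 3.03 (stated: 3.0).

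The inputs agree with one another.

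**2. What the schedule can support.** After 6 h on Day 1, the next scheduled sample is the pre-dose sample on Day 8. The rest (Days 15, 22, 29, 43, 57, 71 and 84) are also pre-dose. Only Day 1, 0 to 6 h, has more than one scheduled sample within a dosing interval. Protocol 6.3 gives a median Tmax of 3.0 h and calls it similar to single dosing, so samples at 1, 3 and 6 h bracket the expected peak. A Day 1 AUC0-24 is not observable.

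**3. Size of AUC0-t on the Day 1 reading.** Single-dose Cmax "ranged from 1010 to 5873 ng/mL across doses". Assume that 5.873 µg/mL belongs to 0.4 mg/kg and that Cmax is linear in dose from 2.533 µg/mL at 0.2 mg/kg.
- At 0.30 mg/kg: 2.533 + 0.5 × 3.340 = 4.203 µg/mL.
- At 0.42 mg/kg (the Table 3 maximum, slightly above the highest dose studied): 2.533 + 1.1 × 3.340 = 6.207 µg/mL.
- Ceiling for AUC over 0 to 6 h = 6 × Cmax = 25.2 to 37.2 h·µg/mL.

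**4. Size on the whole-study reading, without escalation.** Day 1 to Day 84 pre-dose is 83 × 24 = 1,992 h.
- High: 83 × 141.5 = 11,745 h·µg/mL, using the Table 2 AUC0-24 at 0.10 mg/kg.
- Low: the average level is 141.5 / 24 = 5.896 µg/mL, and a linear fall from the Table 2 Cmax gives a pre-dose level of 2 × 5.896 − 6.57 = 5.222. Dropping the first 9 days and taking 90% of that level: 74 × 24 × 0.9 × 5.222 = 8,347 h·µg/mL.
- Ratio to step 3: 8,347 / 37.2 = 224, up to 11,745 / 25.2 = 466.

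**5. What drives the ratio.** Time alone gives 1,992 / 6 = 332. The remaining factor is the average whole-study concentration over the Day 1 ceiling:
- High: 5.896 / 4.203 = 1.40, and 332 × 1.40 ≈ 466.
- Low: (8,347 / 1,992) / 6.207 = 4.19 / 6.207 = 0.675, and 332 × 0.675 ≈ 224.

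The ratio is therefore mostly a comparison of 12 weeks with 6 hours.

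**6. How firm it is.**
- Table 2 also gives 152.8 for 0.14 mg/kg, and 83 × 152.8 = 12,682, so 11,745 is not an upper limit.
- For subjects who stop early, assume a Day 1 peak of 4.5 µg/mL (linear interpolation across the whole single-dose range), fractions of 0.7, 1 and 0.97 of that peak at 1, 3 and 6 h, and pre-dose levels of 5.2 µg/mL (85% of that on Day 8). AUC over 0 to 6 h is then 22.4, and the ratio is about 33 if the last sample is on Day 8, 147 on Day 29 and 224 on Day 43. A ratio above 200 thus needs sampling beyond Day 29.

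**The case for a change.** The strongest case for a change does not need the whole-study calculation. Suppose everyone computes Day 1, 0 to 6 h. An unlabelled AUC0-t of at most 25.2 to 37.2 would then sit 74% to 82% below the Table 2 AUC0-24 (1 − 37.2/141.5 and 1 − 25.2/141.5), and below the Phase 1 Day 1 AUCtau of 50.0 at a lower dose. A reader could mistake a short window for low exposure in patients. Protocol 11.2.9 also plans to compare PK by anti-drug antibody status, and Day 1 parameters precede any antibody response to treatment.

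The part about the label stands: a Day 1, 0 to 6 h title would help a reader. The gap itself is mainly the window. Six hours of the Table 2 average is 141.5 × 6/24 = 35.4, inside the 25.2 to 37.2 range. With 6 to 8 subjects, the listings of collection times with concentrations (16.2.8.1) and of individual parameters (16.2.8.2) let a reader trace each value to its samples. For the antibody comparison, the later pre-dose concentrations are collected and tabulated, so a usable PK measure exists.

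The supplied SAP is also not the last one. It cites protocol version 1.1 of October 2016, while the post-lock amendment builds on SAP Version 3.0. The amendment describes 14.2.11.1 to 14.2.11.3 as concentration and metabolite tables and quotes an existing footnote on post-escalation values; neither matches the supplied SAP's table list. Some dose handling was therefore written in text that was not supplied, and the parameter definitions may be there too.

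**Conclusion.** The observation is correct: the supplied text gives no dose, day or t, and scheduled post-dose sampling covers only 0 to 6 h after the loading dose. It is a gap that an analyst fills sensibly. One serially sampled profile exists, its times suit Cmax and tmax, and AUC0-t (rather than AUC0-24) is a natural name for an area that stops before 24 h. No text promises Cmax, tmax or AUC for a maintenance interval. Maintenance exposure is shown by the planned concentrations before and after escalation, the timing of escalation by visit and the subject-level plots.

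The ratio of about 220 to 470 should carry no weight. It rests on a first-dose-to-Week-12 calculation that no section states, on Phase 1 healthy-volunteer values and model predictions, and mostly on elapsed time. The PK summaries are descriptive, no efficacy result depends on them, and a fuller definition would alter no sample and no conclusion. A Day 1, 0 to 6 h label on Table 14.2.12, if the shells lack one, belongs to table production and is not a change to the plan.
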